5.1.2 Subject Exclusion Criteria

The subject must be excluded from participating in the trial if the subject:

1. Cohort 1: Has triple negative breast cancer, is considered for cohort 1 participation, and received prior anthracycline therapy.
Cohort 2: Has received prior aromatase inhibitor therapy and is deemed to be resistant to all three (anastrozole, letrozole, exemestane) approved AIs. Resistance is defined as progression within 12 months or while on an AI.
2. Patient is premenopausal (see Table 1, medical ovarian suppression is allowed)Is currently participating and receiving study therapy or has participated in a study of an investigational agent and received study therapy or used an investigational device within 4 weeks of the first dose of treatment.
3. Has a diagnosis of immunodeficiency or is receiving systemic steroid therapy or any other form of immunosuppressive therapy within 7 days prior to the first dose of trial treatment.
4. Has a known history of active TB (Bacillus Tuberculosis)
5. Hypersensitivity to pembrolizumab or any of its excipients.
6. Suboptimal cardiac function as defined by decreased left ventricular ejection fraction < 55% for cohort 1, and < 50% for cohort 2.
7. Prior pembrolizumab.
8. Has had a prior anti-cancer monoclonal antibody (mAb) within 4 weeks prior to study Day 1 or who has not recovered (i.e., \leq Grade 1 or at baseline) from adverse events due to agents administered more than 4 weeks earlier.
9. Has had prior chemotherapy, targeted small molecule therapy, or radiation therapy within 2 weeks prior to study Day 1 or who has not recovered (i.e., \leq Grade 1 or at baseline) from adverse events due to a previously administered agent.
 - Note: Subjects with \leq Grade 2 neuropathy are an exception to this criterion and may qualify for the study.

- Note: If subject received major surgery, they must have recovered adequately from the toxicity and/or complications from the intervention prior to starting therapy.

10. Has a known additional malignancy that has progressed or required active treatment in the past 5 years. Exceptions include basal cell carcinoma of the skin or squamous cell carcinoma of the skin that has undergone potentially curative therapy or in situ cervical cancer.
11. Has known active central nervous system (CNS) metastases and/or carcinomatous meningitis. Subjects with previously treated brain metastases may participate provided they are stable (without evidence of progression by imaging for at least four weeks prior to the first dose of trial treatment and any neurologic symptoms have returned to baseline), have no evidence of new or enlarging brain metastases, and are not using steroids for at least 7 days prior to trial treatment. This exception does not include carcinomatous meningitis which is excluded regardless of clinical stability.
12. Has active autoimmune disease that has required systemic treatment in the past 2 years (i.e. with use of disease modifying agents, corticosteroids or immunosuppressive drugs). Replacement therapy (e.g. thyroxine, insulin, or physiologic corticosteroid replacement therapy for adrenal or pituitary insufficiency, etc.) is not considered a form of systemic treatment.
13. Has a history of, active, pneumonitis requiring treatment with steroids or history of/active interstitial lung disease.
14. Has an active infection requiring systemic therapy.
15. Has a history or current evidence of any condition, therapy, or laboratory abnormality that might confound the results of the trial, interfere with the subject's participation for the full duration of the trial, or is not in the best interest of the subject to participate, in the opinion of the treating investigator.
16. Has known psychiatric or substance abuse disorders that would interfere with cooperation with the requirements of the trial.
17. Is pregnant or breastfeeding, or expecting to conceive or father children within the projected duration of the trial, starting with the pre-screening or screening visit through 120 days after the last dose of trial treatment.
18. Has received prior therapy with an anti-PD-1, anti-PD-L1, or anti-PD-L2 agent.
19. Has a known history of Human Immunodeficiency Virus (HIV) (HIV 1/2 antibodies).
20. Has known active Hepatitis B (e.g., HBsAg reactive) or Hepatitis C (e.g., HCV RNA [qualitative] is detected).

21. Has a history of (non-infectious) pneumonitis that required steroids or currently has pneumonitis.

22. Has received a live vaccine within 30 days of planned start of study therapy.

Note: Seasonal influenza vaccines for injection are generally inactivated flu vaccines and are allowed; however intranasal influenza vaccines (e.g., Flu-Mist®) are live attenuated vaccines, and are not allowed.

5.2 Participant Enrollment

5.2.1 Pre-Enrollment Informed Consent and Screening Procedures

Diagnostic or laboratory studies performed exclusively to determine eligibility will be done only after obtaining written informed consent. Studies or procedures that are performed for clinical indications (not exclusively to determine study eligibility) may be used for baseline values and/or to determine pre-eligibility, even if the studies were done before informed consent was obtained. The informed consent process is to be fully documented, and the prospective participant must receive a copy of the signed informed consent document.

5.2.3 Slot verification and reservation

The study team personnel (including physicians, protocol nurses and/or CRCs) may wish to contact the DCC to verify slot availability and to reserve an open slot or be placed in queue for slot opening. Slots may only be held for a limited time which will be determined by the PMT. The Data Coordinating Center should be notified of cancellations of prospective participants holding slots as soon as possible.

5.2.4 Registration procedure

To register a participant, the subsequent procedure is to be followed.

1. The coordinator/research nurse should contact the DCC via telephone or email to provide notification regarding the pending registration and communicate desired timeline of the registration, especially if it must be completed promptly.

2. The coordinator/research nurse should then e-mail copies to [contact] of the following documents to the DCC:

- Completed Eligibility Criteria List (printed from Section 5.1.1 and 5.1.2 of the protocol)
- Source documentation to support eligibility criteria**
- Signed informed consent document
- Signed HIPAA authorization form (if separate from the informed consent document)
- Signed subject's Bill of Rights (COH only)

**For COH participants, provide copies of source documentation only if not readily available as a finalized record in the COH EMR.

3. After having received all documentation, the DCC will complete the review the documents to verify eligibility, working with the staff as needed to resolve any missing required source elements. A subject failing to meet all protocol eligibility requirements will not be registered.

4. Once eligibility has been confirmed, DCC staff will register the participant by assigning a participant study number and will enter the subject into the eCRF system, Medidata RAVE (once dosing is confirmed). The COH CRC will directly accession into MIDAS as per current policy and procedure.

5. Once registration has been completed, DCC staff will send a Confirmation of Registration Form, including the participant study number and cohort assignment to:

- the site study team: site PI, treating physician, biostatistician, protocol nurse, CRC and IDS pharmacy.

5.3 Trial Treatments

The treatment to be used in this trial is outlined below in [Table 2](#)

Table 2 Trial Treatment

Cohort 1 Triple negative breast cancer

Drug	Dose	Dose Frequency	Route of Administration	Regimen/Treatment Period	Use
Pembrolizumab	200 mg	Q3W	IV infusion	Day 1 of each 3 week cycle	Experimental
Doxorubicin*	50-60 mg/m ²	Q3W X 6 cycles	IV infusion	Day 1 of each 3 week cycle, standard	

*starting dose 50 mg/m² for cohort 1, escalating to 60mg/m² based on acceptable toxicity during safety-lead in. see Statistical Section. No intrapatient dose escalation

is allowed. After 6 cycles of doxorubicin and pembrolizumab, patients will continue on pembrolizumab alone up to a total of 24 cycles.

Subjects who stop pembrolizumab with stable disease or better may be eligible for up to one year of additional pembrolizumab therapy if they progress after stopping study treatment.

Cohort 2 HR+ breast cancer

Drug	Dose/Potency	Dose Frequency	Route of Administration	Regimen/Treatment Period	Use
Pembrolizumab	200 mg	Q3W	IV infusion	Day 1 of each 3 week cycle	Experimental
Aromatase inhibitor (AI)*	Exemestane 25 mg daily po preferred, Anastrozole 1 mg daily po, or letrozole 2.5 mg daily po are options	QD	Po	QD cycle, standard	

*pending prior exposure: patients could not have failed all three commercially available AIs.

Trial treatment should begin as close as possible to the date on which treatment is allocated/assigned.

Subjects who stop pembrolizumab with stable disease or better may be eligible for up to one year of additional pembrolizumab therapy if they progress after stopping study treatment.

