1.0 TRIAL SUMMARY

Abbreviated Title	MK-3475 and doxorubicin or an aromatase inhibitor for breast cancer
Trial Phase	Phase II with 2 parallel cohorts; Cohort 1 MK-3475 with doxorubicin and Cohort 2 combines MK-3475 with an aromatase inhibitor; A safety lead-in for the combination of MK-3475 both with doxorubicin or the aromatase inhibitor will be tested.
Clinical Indication	Advanced breast cancer, stage IV
Trial Type	Interventional
Type of control	None
Route of administration	IV MK-3475, IV doxorubicin, oral anti-estrogen (aromatase inhibitor) therapy
Open-label	None
Treatment Groups	Cohort 1 : Triple negative breast cancer Pembrolizumab 200 mg IV every 3 weeks and doxorubicin 50-60 mg/m ² IV every 3 weeks (based on safety lead-in) x 6 cycles followed by a pembrolizumab alone for up to 35 cycles or a maximum of 24 months starting from the first cycle. Cohort 2: HR+ HER2- breast cancer Pembrolizumab 200 mg IV every 3 weeks and anastrozole 1 mg, letrozole 2.5 mg, or exemestane 25 mg (preferred) daily (with a lead-in)
Number of trial subjects	Approximately 60
Estimated enrollment period	24 months
Estimated duration of trial	36 months

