Duration of Participation	
After signing the informed consent form (ICF), passing the screening phase and initiating therapy, patients will participate until death or discontinuation from trial treatment due to progression. Patients discontinuing treatment for reasons other than progression will be followed until progression and treatment-related toxicities have resolved or another treatment regimen is initiated. Treatment with pembrolizumab for patients of the triple negative cohort (treated with 6 cycles of doxorubicin/pembrolizumab) will continue with pembrolizumab until disease progression, treatment-related unacceptable toxicities, intercurrent illness preventing further administration of study drug, subject or investigator's decision to withdraw, pregnancy, or, if a patient receives a total of 24 months of pembrolizumab (including the cycles given with doxorubicin). Patients in the hormone-receptor positive cohort may also receive up to 24 months of pembrolizumab, as well. They can continue on their selected anti-estrogen therapy (whichever aromatase inhibitor was chosen with pembrolizumab) until progression. Patients achieving a confirmed complete response may consider stopping pembrolizumab within a year of such response, and could be retreated within 12 months from stoppage. Subjects who stop pembrolizumab with stable disease or better may be eligible for up to one year of additional pembrolizumab therapy if they progress no sooner than 8 weeks after stopping study treatment, for either cohort.
 
After the end of treatment patients will be followed for 30 days for adverse event (AE) monitoring and serious adverse events (SAEs) and events of clinical interest will be collected for 90 days after the end of treatment, or 30 days after the end of treatment if a patient initiates new anti-cancer therapy or until the treatment toxicities clearly stabilize or resolve (whichever is first).

[figure not shown]

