5.9 Subject Withdrawal/Discontinuation Criteria

Subjects may withdraw consent at any time for any reason or be dropped from the trial at the discretion of the investigator should any untoward effect occur. In addition, a subject may be withdrawn by the investigator or the Sponsor if enrollment into the trial is inappropriate, the trial plan is violated, or for administrative and/or other safety reasons. Specific details regarding discontinuation or withdrawal are provided in Section 7.1.3 – Other Procedures.

A subject must be discontinued from the trial for any of the following reasons:

- The subject or legal representative (such as a parent or legal guardian) withdraws consent.
- Confirmed radiographic disease progression

Note: For unconfirmed radiographic disease progression, please see Section 4.1.5.1

Note: A subject may be granted an exception to continue on treatment with confirmed radiographic progression if clinically stable or clinically improved, please see Section 4.1.5.1

- Unacceptable adverse experiences as described in Section 5.2.1.2
- Intercurrent illness that prevents further administration of treatment

- Investigator's decision to withdraw the subject
- The subject has a confirmed positive serum pregnancy test
- Noncompliance with trial treatment or procedure requirements
- The subject is lost to follow-up
- Completed 24 months of uninterrupted treatment with pembrolizumab or 35 administrations of study medication, whichever is later.

Note: 24 months of study medication is calculated from the date of first dose. Subjects who stop pembrolizumab after 24 months may be eligible for up to one year of additional study treatment if they progress after stopping study treatment provided they meet the requirements detailed in Section 7.1.4.5

- Administrative reasons

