7.1.2.8.2 Blood Collection for Anti-Pembrolizumab Antibodies NA

7.1.3 Other Procedures

7.1.3.1 Withdrawal/Discontinuation

When a subject discontinues/withdraws prior to trial completion, all applicable activities scheduled for the final trial visit should be performed at the time of discontinuation. Any adverse events which are present at the time of discontinuation/withdrawal should be followed in accordance with the safety requirements outlined in Section 7.2 - Assessing and Recording Adverse Events. Subjects who a) attain a CR or b) complete 24 months of treatment with pembrolizumab may discontinue treatment with the option of restarting treatment if they meet the criteria specified in Section 7.1.4.5. After discontinuing treatment following assessment of CR, these subjects should return to the site for a Safety Follow-up Visit (described in Section 7.1.5.3.1) and then proceed to the Follow-Up Period of the study (described in Section 7.1.5.4).

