7.1.4.5 Second Course Phase (Retreatment Period)

Subjects who stop pembrolizumab with SD or better may be eligible for up to one year of additional pembrolizumab therapy if they progress after stopping study treatment. This retreatment is termed the Second Course Phase of this study and is only available if the study remains open and the subject meets the following conditions:

- **Either**
 - Stopped initial treatment with pembrolizumab after attaining an investigator-determined confirmed CR according to RECIST 1.1, and
 - Was treated for at least 24 weeks with pembrolizumab before discontinuing therapy and has not progressed within 8 weeks of completion of such therapy, but not beyond 12 months of being off therapy.
 - Received at least two treatments with pembrolizumab beyond the date when the initial CR was declared

OR

- Had SD, PR or CR and stopped pembrolizumab treatment after 24 months of study therapy for reasons other than disease progression or intolerance

AND

- Experienced an investigator-determined confirmed radiographic disease progression after stopping their initial treatment with pembrolizumab
- Did not receive any anti-cancer treatment since the last dose of pembrolizumab
- Has a performance status of 0 or 1 on the ECOG Performance Scale
- Demonstrates adequate organ function as detailed in Section 5.1.2
- Female subject of childbearing potential should have a negative serum or urine pregnancy test within 72 hours prior to receiving retreatment with study medication.
- Female subject of childbearing potential should be willing to use 2 methods of birth control or be surgically sterile, or abstain from heterosexual activity for the course of the study through 120 days after the last dose of study medication (Reference Section 5.7.2). Subjects of child bearing potential are those who have not been surgically sterilized or have been free from menses for > 1 year.
- Male subject should agree to use an adequate method of contraception starting with the first dose of study therapy through 120 days after the last dose of study therapy.

- Does not have a history or current evidence of any condition, therapy, or laboratory abnormality that might interfere with the subject's participation for the full duration of the trial or is not in the best interest of the subject to participate, in the opinion of the treating investigator.

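### The Cohort 1 note to Table 2 caps pembrolizumab at 24 cycles (16.6 months), while the rest of the protocol plans 24 months or 35 doses

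*Combined protocol and SAP*

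**What the plan says.** Section 5.3 sets out the trial treatment in Table 2. The Cohort 1 note there reads: "After 6 cycles of doxorubicin and pembrolizumab, patients will continue on pembrolizumab alone up to a total of 24 cycles". The note then adds that a patient who stops with stable disease or better and later progresses may be eligible for up to a further year of pembrolizumab. The Cohort 2 part of the table carries the same retreatment sentence but no cycle cap.

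Elsewhere the duration is longer:

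- Section 1.0, Treatment Groups, Cohort 1: "followed by a pembrolizumab alone for up to 35 cycles or a maximum of 24 months starting from the first cycle".
- Section 1.0, Duration of Participation: the triple negative cohort continues until progression or another listed event, or "if a patient receives a total of 24 months of pembrolizumab (including the cycles given with doxorubicin". For Cohort 2: "Patients in the hormone-receptor positive cohort may also receive up to 24 months of pembrolizumab, as well".
- Section 5.9, reasons for mandatory discontinuation: "Completed 24 months of uninterrupted treatment with pembrolizumab or 35 administrations of study medication, whichever is later", with the note that "24 months of study medication is calculated from the date of first dose".
- Section 7.1.3.1: subjects who "a) attain a CR or b) complete 24 months of treatment with pembrolizumab may discontinue treatment with the option of restarting treatment".
- Section 7.1.4.5, the only retreatment route that does not need a complete response: "Had SD, PR or CR and stopped pembrolizumab treatment after 24 months of study therapy for reasons other than disease progression or intolerance".

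**The concern.** A Cohort 1 patient who has not progressed by the end of cycle 24 must stop under the Table 2 note, yet continues under Section 1.0 and meets no stopping criterion in Section 5.9. Whichever the site does departs from some current text.

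Two things are at stake for that patient. One is the remaining planned doses. The other is the Second Course: Section 7.1.4.5 requires 24 months of therapy unless the patient stopped after a confirmed complete response. A patient in stable disease or partial response who stops at cycle 24 cannot meet that condition, although the next sentence of the same note holds out retreatment to such patients. The complete-response route stays open, because it needs only 24 weeks of pembrolizumab and two doses after the response.

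**Working it through.** **Inputs.** The cycle length is 21 days (Table 2). The limits are those listed above. A month is 365.25 / 12 = 30.44 days.

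**The plan's own pairing of 35 doses with 24 months.** 35 × 21 = 735 days, and 735 / 30.44 = 24.1 months. In reverse, 24 × 30.44 / 21 = 34.8 cycles, which rounds to 35. The two figures agree with each other.

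**The Table 2 note against that.**

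| Reading | Cycles | Days | Weeks | Months | Doses short of 35 |
|---|---|---|---|---|---|
| 24 cycles in total | 24 | 504 | 72 | 16.6 | 11 (33 weeks) |
| 24 cycles after the first 6 | 30 | 630 | 90 | 20.7 | 5 (15 weeks) |
| Sections 1.0 and 5.9 | 35 | 735 | 105 | 24.1 | 0 |

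Neither reading of the note reaches 24 months.

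**Patients who would lose doses.** The documents give no estimate of progression-free survival for this regimen, so the share reaching cycle 24 without progression is assumed to be 5-20%. Then 36 × 0.05 = 1.8 and 36 × 0.20 = 7.2, or about 2 to 7 of 36.

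**Patients who would lose retreatment.** These are patients who would otherwise have reached 24 months and later progressed while the study was open.

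- Section 1.0 estimates 24 months of enrolment and a 36-month trial. Assuming even accrual, only patients enrolled by month 12 can complete 24 months: 36 × 12/24 = 18.
- Carrying the 5-20% from 16.56 to 24 months at a constant hazard: 0.05^(24/16.56) = 0.013 and 0.20^(24/16.56) = 0.097.
- 18 × 0.013 = 0.2 and 18 × 0.097 = 1.7.
- With the 18-month accrual that Section 8.2.1 also allows, 36 × 12/18 = 24 patients, giving 0.3 to 2.3.

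These are upper figures. The patient must still progress before closure, have ECOG 0 or 1 and have had no other anticancer treatment. A patient who completes 24 months just at closure has no time to re-enter. Patients with a confirmed complete response may keep their own route.

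**Primary analysis.** The Cohort 1 rule (at least 4 responses in 22, then 9 in 36) has an exact type I error of 0.077 at a 15% response rate and power of 0.900 at 34%. Treatment duration is not an input to either figure.

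**Delayed doses: Section 1.0 against Section 5.9.** With no delay the 35th dose falls 34 × 21 = 714 days after the first.

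- After a 3-week delay it falls at 735 days, just past 24 months (730.5 days). A 24-month maximum then allows 34 doses, a difference of 1.
- After a 12-week delay it falls at 798 days (26.2 months). A 24-month maximum then allows 31 doses, a difference of 4.

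**The case against.** The strongest reply is that this is a one-word slip that nobody would act on. Several sections agree against one phrase, the phrase sits in the footnote to the doxorubicin row, the pembrolizumab row has no cap, and the mandatory stopping list in Section 5.9 does not mention 24 cycles. The same note also mentions retreatment, so it does not plainly remove it. A slip is indeed the likeliest explanation. But the sentence is a current treatment-duration rule in the section that defines trial treatment, and no text says that another section overrides it. The retreatment sentence does not rescue the patient, because Section 7.1.4.5 attaches the 24-month condition.

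Three stronger readings are tempting and are not supported:

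- A reader might infer that one to three patients lose retreatment, by assuming that 5-15% are still without progression at 24 months. Set beside 5-20% at 16.6 months, the equal low ends imply no progression or dropout over more than seven months. The constant-hazard figures above are the better guide.
- A reader might infer that the later-of-the-two rule in Section 5.9 should simply be imposed everywhere. Section 1.0 states 24 months as a maximum or total for both cohorts. The Section 5.9 rule would permit dosing to 26.2 months after a 12-week delay. Section 1.0 does not plan those doses, and allowing them is a sponsor decision on exposure.
- A reader might infer damage to the efficacy conclusions. The response rules do not depend on duration. Any effect on progression-free survival or time to treatment failure is confined to follow-up after week 72, and the Kaplan-Meier medians do not change if fewer than half of the patients get that far.

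**Conclusion.** The concern holds as a contradiction in treatment duration. The Table 2 note's 24 cycles agree with neither the 24 months nor the 35 doses stated elsewhere, on either way of counting the cycles. A patient held to the note loses up to 11 doses (5 on the 30-cycle reading), and one in stable disease or partial response also loses access to the Second Course.

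The number affected is small. The 2 to 7 of 36 rests wholly on the assumed 5-20%. The figure of fewer than about 2 for retreatment rests on that assumption, a constant hazard, even accrual over 24 months and closure at month 36. The faster accrual raises the upper end to 2.3 before the further entry conditions are applied. Cohort 2 is not affected by the note. The point deserves correction because it concerns how long individual patients are treated, not because it threatens the trial's conclusions.

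**What to change.** In the Cohort 1 note to Table 2, replace the 24-cycle limit with *up to a total of 24 months from the first dose (35 administrations), counting the six cycles combined with doxorubicin; see Section 5.9*.

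Separately, and minor, the sponsor should settle two points and then use the same wording throughout:

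1. For patients with delayed doses, choose between the 24-month maximum in Section 1.0 and the later-of-the-two rule in Section 5.9.
2. Decide whether the 8-week minimum before progression applies to both retreatment branches, as Duration of Participation in Section 1.0 has it, or only to the complete-response branch, as in Section 7.1.4.5.

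The cost is wording in one amendment, with no added patients or procedures. Cohort 1 patients still on treatment at cycle 24 would receive up to 11 further doses, all within the 24 months or 35 doses already planned in Sections 1.0 and 5.9. Choosing the later-of-the-two rule could add doses beyond 24 months in either cohort, which is why it is left to the sponsor.
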